6.1.12 Dabrafenib or Dabrafenib + Trametinib Dose Modification for QTc Prolongation

Table 6-8: Dabrafenib + Trametinib modification for QTc Prolongation

Prolongation	Action and Dose Modification
• QTcB \geq 501 msec	
 Interrupt study treatment until QTcB prolongation resolves to grade 1 or baseline. Test serum potassium, calcium, phosphorus and magnesium. If abnormal, correct per routine clinical practice to within normal limits. Review concomitant medication usage for agents that prolonged QTc. If the event resolves, restart study treatment at current dose level.^b If the event does not resolve, permanently discontinue study treatment. Consider evaluation with cardiologist. If the event recurs, permanently discontinue study treatment. Consider evaluation with cardiologist.

Abbreviations: msec = milliseconds; QTcB = QT interval on electrocardiogram corrected using the Bazett's formula
 a. Based on average QTc value of triplicate ECGs. For example, if an ECG demonstrates a prolonged QT interval, obtain two or more ECGs over a brief period, and then use the averaged QTc values of the three ECGs to determine if study treatments should be interrupted or discontinued.
 b. If the QTc prolongation resolves to grade 1 or baseline, the subject may resume study treatment if the investigator and CTEP medical monitor agree that the subject will benefit from further treatment.

6.1.13 Dabrafenib or Dabrafenib + Trametinib Dose Modification for Diarrhea

Episodes of diarrhea have been observed in patients receiving dabrafenib, trametinib, or both therapies in combination. Other, frequent causes for diarrhea including concomitant medications (e.g., stool softeners, laxatives, antacids, etc.), infections caused by *C. difficile* or other pathogens, partial bowel obstruction, etc., should be clinically excluded.

Table 6-9: Dabrafenib or Dabrafenib + Trametinib Treatment Modification and Management Guidelines for Diarrhea

CTCAE Grade	Management Guideline	Action and Dose Modification
Uncomplicated Diarrhea,¹ Grade 1 or 2 (tolerable)	
 Diet: Stop all lactose containing products; eat small meals, BRAT-diet (banana, rice, apples, toast) recommended. Hydration: 8-10 large glasses of clear liquids per day (e.g., Gatorade or broth). Loperamide³: Initially 4 mg, followed by 2 mg every 4 hours or after every unformed stool; maximum 16 mg/day. Continue until diarrhea-free for 12 hours. Diarrhea >24 hours: Loperamide 2 mg every 2 hours; maximum 16 mg/day. Consider adding oral antibiotics. Diarrhea >48 hours: Loperamide 2 mg every 2 hours; maximum 16 mg/day. Add budesonide or other second-line therapies (otreotide, or tincture of opium) and oral antibiotics. 	
 Continue study treatment. If diarrhea is grade 2 for > 48 hours, interrupt study treatment until diarrhea resolves to grade \leq 1. Restart study treatment at the same dose level.
Uncomplicated Diarrhea,¹ Grade 2 (intolerable), 3, or 4	
 Clinical evaluation mandatory. Loperamide³: Initially 4 mg, followed by 2 mg every 4 hours or after every unformed stool; maximum 16 mg/day. Continue until diarrhea-free for 12 hours. 	
 Interrupt study treatment until diarrhea resolves to \leq grade 1. Restart with study treatment reduced by one dose level.⁴
Any Complicated Diarrhea²	
 Oral antibiotics and second-line therapies if clinically indicated Hydration: Intravenous fluids if clinically indicated. Antibiotics (oral or intravenous) if clinically indicated. Intervention should be continued until the subject is diarrhea-free for \geq 24 hours. Intervention may require hospitalization for subjects at risk of life-threatening complications. 	
 If 3 dose reductions of study treatment are clinically indicated, permanently discontinue study treatment.

1. **Uncomplicated diarrhea** defined by the absence of symptoms such as cramping, nausea/vomiting, \geq grade 2, decreased performance status, pyrexia, sepsis, neutropenia \geq grade 3, frank bleeding, and/or dehydration requiring intravenous fluid substitution.

2. **Complicated diarrhea** defined by the presence of symptoms such as cramping, nausea/vomiting, \geq grade 2, decreased performance status, pyrexia, sepsis, neutropenia \geq grade 3, frank bleeding, and/or dehydration requiring intravenous fluid substitution.

3. Loperamide should be made available prior to start of study treatment so loperamide administration can begin at the first signs of diarrhea.

4. Escalation of study treatment to previous dose level is allowed after consultation with the medical monitor and in the absence of another episode of complicated or severe diarrhea in the 4 weeks subsequent to dose reduction.

6.1.14 Dabrafenib or Dabrafenib + Trametinib Dose Modification for Vision Changes

Episodes of vision changes have been observed in patients receiving dabrafenib, trametinib, or the combination of both therapies. An ophthalmologist should be consulted if changes in vision

develop. However, if the visual changes are clearly unrelated to study treatment (e.g., allergic conjunctivitis), then monitor closely as it may be reasonable to defer ophthalmic examination.

Uveitis and iritis have been associated with dabrafenib, while RPED and RVO have been associated with trametinib therapy. Monitor patients for visual signs and symptoms (such as change in vision, photophobia, and eye pain) during therapy. Special attention should be given to retinal findings (e.g., retinal pigment epithelial detachment (RPED) or retinovascular abnormalities (i.e., branch or central retinal vein occlusions [RVO]). For events of visual changes regardless of severity but for which an ophthalmic examination is conducted, a blood sample for PK analysis is encouraged when feasible, and the blood sample should be drawn as close as possible to the time of the event.

The ophthalmology exam will include best corrected visual acuity, visual field examination, tonometry, slit lamp biomicroscopic examination of the anterior segment (with special attention to inflammation) and the posterior segment, and dilated indirect fundoscopy with special attention to retinal abnormalities. Optical coherence tomography is strongly recommended at scheduled visits and if retinal abnormalities are suspected. Other types of ancillary testing including color fundus photography, and fluorescein angiography may also be indicated as determined by clinical exam.

Guidelines regarding event management and dose reduction for visual changes considered to be related to study treatment are provided in the table below.

Table 6-10: Dabrafenib or Dabrafenib-Trametinib Treatment Modification for Visual Changes

CTCAE Grade	Management Guideline	Action and Dose Modification
Grade 1	
 Consult ophthalmologist immediately. 	
 If dilated fundus examination cannot be performed within 7 days of onset, hold trametinib until RPED and RVO can be excluded by retina specialist/ophthalmologist. Dabrafenib may be continued. If RPED and RVO excluded, continue (or restart) trametinib at same dose level If Uveitis/Iritis, refer to table below for Iritis/Uveitis If RPED suspected or diagnosed, refer to RPED dose modification table below; report as SAE if diagnosed. If RVO suspected or diagnosed: Permanently discontinue trametinib and report as SAE if diagnosed.

CTCAE Grade	Management Guideline	Action and Dose Modification
Grade 2 and 3	
 Consult ophthalmologist immediately. 	
 Hold trametinib. Dabrafenib may be continued. If RPED and RVO excluded, restart trametinib at same dose level If Uveitis/Iritis, refer to table below for Uveitis/Iritis If RPED diagnosed, see RPED dose modification table below; report as SAE. If RVO diagnosed: Permanently discontinue trametinib and report as SAE.
Grade 4	
 Consult ophthalmologist immediately. 	
 Interrupt trametinib. Dabrafenib may be continued. If RPED and RVO excluded, may consider restarting trametinib at same or reduced dose after discussion with study medical monitor. If Uveitis/Iritis, refer to table below If RVO or RPED diagnosed, permanently discontinue trametinib and report as SAE.

Abbreviations: RPED = retinal pigment epithelial detachments; RVO = retinal vein occlusion; SAE = serious adverse event
 *If visual changes are clearly unrelated to study treatment (e.g., allergic conjunctivitis), monitor closely but ophthalmic examination is not required

Table 6-11: Dose Modification for RPED

Event CTCAE Grade	Action and Dose Modification
Grade 1 RPED (Asymptomatic; clinical or diagnostic observations only)	
 Continue trametinib with retinal evaluation monthly until resolution. If RPED worsens, follow instructions below. Dabrafenib treatment is not affected
Grade 2-3 RPED (Symptomatic with mild to moderate decrease in visual acuity; limiting instrumental ADL)	
 Interrupt trametinib. Continue dabrafenib Retinal evaluation monthly. If improved to \leq Grade 1, restart trametinib with one dose level reduction (reduced by 0.5 mg) or discontinue in patients taking trametinib 1 mg daily. If no recovery within 4 weeks permanently discontinue trametinib

Table 6-12: Dabrafenib or Dabrafenib-Trametinib Dose Modification for Uveitis and Iritis

CTCAE Grade	Action and Dose Modification
Uveitis and Iritis	
 Continue study treatment Control ocular inflammation with local therapies If not improved to grade ≤ 1 within 1 week, interrupt dabrafenib until resolution of ocular inflammation and then restart dabrafenib reduced by one dose level If no recover within 4 weeks, permanently discontinue dabrafenib. Trametinib may be continued.

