6.1.15 Dabrafenib + Trametinib Dose Modification for Pneumonitis

Pneumonitis has been observed in patients receiving trametinib in combination with dabrafenib. To reduce the risk of pneumonitis, patients will be monitored closely for symptoms, evaluated with imaging and functional tests when appropriate.

Table 6-13: Dabrafenib-Trametinib Treatment Modification for Pneumonitis

CTCAE Grade	Adverse Event Management	Action and Dose Modification
Grade 1	
 CT scan (high-resolution with lung windows) recommended. Clinical evaluation and laboratory work-up for infection. Monitoring of oxygenation via pulse-oximetry recommended. Consultation with pulmonologist recommended. 	Continue study treatment at current dose
Grade 2	
 CT scan (high-resolution with lung windows). Clinical evaluation and laboratory work-up for infection. Consult pulmonologist. Pulmonary function tests: If $<$ normal, repeat every 8 weeks until \geq normal. Bronchoscopy with biopsy and/or BAL recommended Symptomatic therapy including corticosteroids if clinically indicated. 	
 Interrupt trametinib until recovery to grade ≤ 1. Restart with trametinib reduced by one dose level. Escalation to previous dose level after 4 weeks and consultation with the CTEP Medical Monitor may be considered. If no recovery to grade ≤ 1 within 4 weeks, permanently discontinue trametinib.
Grade 3	
 Same as grade 2 	
 Interrupt study treatment until recovery to grade ≤ 1. Resumption of trametinib at one dose level reduction may be considered after consultation with the CTEP Medical Monitor If no recovery to grade ≤ 1 within 4 weeks, permanently discontinue trametinib.
Grade 4	
 Same as grade 2 	Permanently discontinue trametinib.

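### Table 6-10 treats suspected but undiagnosed RVO more severely at Grade 1 than at Grades 2 to 4, and its Grade 1 cell conflicts with itself

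*Combined protocol and SAP*

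**What the plan says.** Table 6-10 in Section 6.1.14 sets the action for visual changes by grade.

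- **Grade 1.** If a dilated fundus examination cannot be done within 7 days of onset, sites are to "hold trametinib until RPED and RVO can be excluded by retina specialist/ophthalmologist". A later bullet reads "If RPED and RVO excluded, continue (or restart) trametinib at same dose level". The last bullet reads "If RVO suspected or diagnosed: Permanently discontinue trametinib and report as SAE if diagnosed".
- **Grades 2 and 3.** "Hold trametinib. Dabrafenib may be continued. If RPED and RVO excluded, restart trametinib at same dose level". The permanent stop is tied to diagnosis: "If RVO diagnosed: Permanently discontinue trametinib and report as SAE".
- **Grade 4.** Trametinib is interrupted. A restart at the same or a lower dose may be considered, after discussion with the medical monitor, if RPED and RVO are excluded. The permanent stop is again tied to diagnosis: "If RVO or RPED diagnosed, permanently discontinue trametinib and report as SAE".

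Table 6-13 in Section 6.1.15 covers pneumonitis. The Grade 3 row says "Interrupt study treatment until recovery to grade" 1 or less and then describes resumption of trametinib only. The sole instruction in the Grade 4 row is to "permanently discontinue trametinib". It does not mention dabrafenib.

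**The concern.** Dose-modification tables normally become stricter, or at least no looser, as grade rises. In Table 6-10 the order runs the other way for a patient whose RVO is suspected but not diagnosed. Within the Grade 1 cell, one bullet ends trametinib on suspicion, while another lets it continue or restart once RVO is ruled out. A patient whose suspicion is later overturned meets both.

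What is at stake is consistency of treatment. Two sites could read the same cell and either end trametinib for good or resume it at the same dose. Section 5.1 defines each dose level as a triplet, and Section 13.1 judges it on cycle 1 in cohorts of 3 to 6, so it matters that all sites apply one rule. The introductory text on dose escalation also gives possible overlapping ocular toxicity of trametinib and AT13387 as the reason for the starting trametinib dose. The ocular rules are therefore not peripheral here.

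**Working it through.** The plan states no figure on this point and no arithmetic decides it. The check sets the rows side by side.

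**Step 1. Trametinib action in Table 6-10, by state of the RVO question.**

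| Grade | RVO suspected, not diagnosed | RPED and RVO excluded | RVO diagnosed |
|---|---|---|---|
| 1 | Permanent stop (a separate bullet holds the drug if the fundus examination is delayed beyond 7 days) | Continue or restart, same dose | Permanent stop |
| 2-3 | Hold | Restart, same dose | Permanent stop |
| 4 | Interrupt | Restart may be considered, same or reduced dose, after discussion with the medical monitor | Permanent stop |

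The last column is the same at every grade. The middle column becomes more cautious with grade. Only the suspected column is inverted: permanent at Grade 1, temporary at Grades 2-3 and 4.

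**Step 2. Is the word for suspicion just loose drafting?** The Grade 1 bullet requires an SAE report only on diagnosis. It therefore separates suspicion from diagnosis and stops trametinib for both. The parallel RPED bullet in that row also covers suspicion, but it only refers the reader to Table 6-11, so it creates no such conflict.

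**Step 3. Does another rule settle it?** The opening of Section 6 and the general guidance in Section 6.1 concern which agent to modify, by attribution and severity. The footnote to Table 6-10 concerns changes clearly unrelated to treatment. None of these alters the RVO trigger.

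**Step 4. Pneumonitis, Table 6-13, by drug.**

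| Grade | Trametinib | Dabrafenib |
|---|---|---|
| 1 | Continue | Continue |
| 2 | Interrupt | Not stated |
| 3 | Interrupt | Interrupt, as part of study treatment |
| 4 | Permanent stop | Not stated |

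Trametinib escalates in order. Dabrafenib has an instruction at Grade 3 and none at Grade 4. Table 6-1 does not fill the gap, because it covers only toxicities not specified in later sections. Silence is not the protocol's habit for severe events: dabrafenib has a stated action for Grade 4 hemorrhage (Table 6-4), symptomatic LVEF decrease (Table 6-6), Grade 4 visual changes (Table 6-10) and life-threatening pulmonary embolism (Section 6.1.17).

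**Step 5. What the documents say about frequency.** Section 2.2.3.4 reports visual symptoms on AT13387, generally Grade 1, in around half of subjects at 150 or 180 mg/m² weekly and in 5 of 7 (5/7 = 71%) at 220 mg/m² weekly. Section 2.2.2.4 reports ocular events in 25% on dabrafenib/trametinib 150/2. Section 2.2.1.3 reports four RVO cases with trametinib as of 22 May 2012. The first two figures suggest that the Grade 1 row will be consulted often. None gives the share of patients in whom RVO is suspected.

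**The case against.** The best defence of the Grade 1 cell is to read its bullets in sequence: consult, hold if the examination is delayed, then act on the result, which is either exclusion or RVO suspected or diagnosed. On that reading, suspicion is a finding of the examination and does not overlap with exclusion. This is a fair reading, and it narrows the conflict inside the cell to patients whose suspicion is overturned later. It does not remove that case, and it does nothing about the inversion against Grades 2-3 and 4.

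On pneumonitis, the focus on trametinib fits the protocol's own attribution. Section 2.2.2.4 lists pneumonitis as a MEK-category event and reports none in 365 subjects in the combination study, and the dabrafenib list in Section 7.1.1.2 does not include it. Section 6 modifies every agent when attribution is unclear, and Section 6.1 points to the CTEP drug monitors for such questions. These provisions weaken any safety argument considerably, though they do not fill the Grade 4 row.

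It is also true that diagnosed RVO is rare in the data the protocol cites. Those cases do not bound the number of suspected ones.

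**Conclusion.** Table 6-10 is inconsistent as written. For suspected but undiagnosed RVO, Grade 1 is harsher than Grades 2-3 and Grade 4, and the Grade 1 cell conflicts with itself when the suspicion is later excluded. The finding rests on the text alone and is limited to suspected RVO. It is worth correcting at the next amendment.

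A reader might infer three stronger things that the documents do not support.

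- **That Table 6-13 is inverted too, and a direct safety risk.** Trametinib is strictest at Grade 4. The row omits dabrafenib; it does not say to continue it. The Grade 3 row speaks of study treatment in a table titled for dabrafenib and trametinib, and AT13387 has its own rule in Table 6-15, which interrupts it at Grades 3 and 4. What remains is a minor omission for dabrafenib.
- **That a countable number of patients will be affected.** This would need an assumed share of visual symptoms that raise suspicion of RVO, and the documents offer no basis for one.
- **That MTD selection is affected.** A route exists. Section 5.2 does not clearly make a Grade 1 event a DLT, and the replacement rule in Section 13.1 for stopping in cycle 1 covers reasons other than toxicity. A patient taken off trametinib on suspicion might therefore count as DLT-free. No frequency is given, and no effect on sample size or escalation probabilities has been shown.

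**What to change.** The sponsor and CTEP should reconcile the Grade 1 RVO bullet in Table 6-10 with the other Grade 1 bullets and with the Grade 2-3 and Grade 4 rows, so that suspected and diagnosed RVO each have one consistent action, including when a suspicion is later excluded. In the same amendment, the scope of the Grade 3 and Grade 4 rows of Table 6-13 should be reconciled so that the position of dabrafenib at Grade 4 is stated. Which action is right is a clinical decision for the sponsor and CTEP, and nothing here favors one. No AT13387 entry is needed in Table 6-13. The cost is wording in two tables, with no added procedures, visits or patients.

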5.2 Definition of Dose Limiting Toxicity

Dose-limiting toxicity (DLT) is based on the CTEP Active Version 5 of the NCI Common Terminology Criteria for Adverse Events (CTCAE). DLT refers to toxicities experienced during the first cycle of treatment between days 1-28. A DLT must be considered to be at least possibly related to study drug(s) will be defined as follows:

- Any grade 4 toxicity
- Grade 3 (or grade 2 intolerable) non-hematologic toxicity
- Grade ≥ 3 neutropenia with fever $> 38.5^{\circ}\text{C}$
- Grade 3 thrombocytopenia with clinically significant bleeding
- Furthermore, grade 2 intolerable/grade 3 fatigue that results in hospitalization should be considered a DLT.
- Intolerable AEs are toxicities deemed to lead to a missing dose of AT13387 or more than 25% of dabrafenib/trametinib in the first cycle.

In general, all Grade 3 or intolerable grade 2, non-hematological toxicities regardless of duration are considered DLT. However, the following Grade 3 toxicities will not be considered a DLT.

- The appearance of cutaneous squamous cell carcinoma or keratoacanthoma will not be considered a dose limiting toxicity as these are commonly observed with dabrafenib.
- Grade 3 fatigue persistent for ≤ 7 days
- Grade 3 nausea, vomiting, or diarrhea persisting ≤ 72 hours with maximum supportive care
- Grade 3 electrolyte events if they are resolved with replacement within 24 hours
- Lymphopenia regardless of grade
- The following grade 3 laboratory abnormalities will not be considered dose limiting if they return to baseline within 7 days: elevated bilirubin, AST, ALT, cholesterol, amylase, lipase, creatinine and hypertriglyceridemia

Management and dose modifications associated with the above adverse events are outlined in Section 6.

Dose escalation will proceed within each cohort according to the following scheme. Dose-limiting toxicity (DLT) is defined above.

Table 5.2. Dose escalation table

Number of Patients with DLT at a Given Dose Level	Dose Escalation Rule
0 out of 3	Proceed to the next dose level and enroll 3 patients
1 out of 3	Enroll and treat 3 additional patients at this dose level.
≥ 2 out of 3	Dose escalation will be stopped. The MTD will be one dose below this dose level. Three (3) additional patients will be entered at the next lower dose level if only 3 patients were treated previously at that dose.
1 out of 6	Proceed to the next dose level.

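### Table 6-12 has one ungraded rule for uveitis and iritis, so dabrafenib need not be held at onset of a Grade 3-4 event, although the protocol's default table would interrupt it

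*Combined protocol and SAP*

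**What the plan says.** The introduction to Section 6.1.14 assigns ocular events to drugs: "Uveitis and iritis have been associated with dabrafenib, while RPED and RVO have been associated with trametinib therapy". Table 6-10 then grades visual changes. At Grade 2-3 trametinib is held and at Grade 4 it is interrupted. In every grade row the position on dabrafenib is "Dabrafenib may be continued", and every row sends uveitis or iritis on to Table 6-12.

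Table 6-12 has a grade column but only one row, with no grade in it. Study treatment goes on, with the instruction "Control ocular inflammation with local therapies". If the event has not improved to grade 1 or lower, the row continues: "within 1 week, interrupt dabrafenib until resolution of ocular inflammation and then restart dabrafenib reduced by one dose level". Without recovery in 4 weeks dabrafenib stops permanently, and trametinib may go on.

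Section 5.2 counts a Grade 3 event as a DLT under "Grade 3 (or grade 2 intolerable) non-hematologic toxicity", and counts any Grade 4 toxicity, if at least possibly related and in cycle 1. It adds: "Management and dose modifications associated with the above adverse events are outlined in Section 6".

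**The concern.** Uveitis is on the protocol's list of dabrafenib adverse events of special interest (Section 2.2.2.4), and the dabrafenib risk list in Section 7.1.1.2 places it among rare but serious events. Yet at Grade 3-4 the required response of the associated drug is weaker than for a toxicity the protocol does not name. A cycle 1 event severe enough to be a DLT is sent to Section 6 for management, and the uveitis rule found there asks for no dabrafenib hold at onset. What is at stake is further dosing with the associated drug early in a serious eye event. It is a patient-safety matter and does not touch the trial's estimates.

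**Working it through.** The first four steps compare rules, so no arithmetic applies to them. The plan gives no figure for this event's frequency in the trial; steps 5 to 7 size it.

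1. **Route.** Grade 1, Grade 2-3 and Grade 4 rows of Table 6-10 all lead, for uveitis or iritis, to the one row of Table 6-12.

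2. **Required dabrafenib action at onset of Grade 3-4.**
   - Table 6-12: continue; hold only after 1 week without improvement to grade 1 or lower.
   - Table 6-1: interrupt at Grade 3; interrupt or permanently discontinue at Grade 4. It covers only toxicities not specified later, so naming uveitis in Table 6-12 takes the event out of it.
   - Table 6-11, for comparison: at Grade 2-3 RPED the associated drug is held at once, "Interrupt trametinib. Continue dabrafenib".

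3. **Do other provisions require a hold?** Section 5.4 lets treatment end for unacceptable adverse events. The opening of Section 6 modifies each agent when the responsible one is hard to identify. Section 6.1 bases modification on nature, severity and attribution. All permit an earlier dabrafenib hold and none requires it. Section 6.2.1.1 requires an ophthalmology visit within 24 hours of a first visual disturbance and sends ocular toxicity to the table above it. It prints that table as 6-13, which is the pneumonitis table; the table above is 6-15. Table 6-15 interrupts treatment at Grade 3 and 4, but it is the AT13387 table and sets no dabrafenib hold.

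4. **Trametinib.** Table 6-10 has already held it at Grade 2-4. At Grade 4, once RPED and RVO are excluded, the investigator "may consider restarting trametinib at same or reduced dose after discussion with study medical monitor". Table 6-12 then says to continue study treatment. It does not say whether that restarts trametinib at once or on Table 6-10's terms.

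5. **Exposure in the gap.** 7 days × 2 doses = 14 dabrafenib doses.

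6. **Frequency.** Section 2.2.2.4 reports 2 Grade 3 cases and 1 Grade 4 case of uveitis in its paragraph on 365 patients given the dabrafenib-trametinib doublet. Rate p = 3/365 = 0.0082, exact 95% CI 0.0017 to 0.0238. Section 13.2 plans 4 to 32 evaluable patients, with 14 in the expansion cohort. Expected cases = N × p; chance of at least one = 1 − (1 − p)^N.

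| N | Expected cases (range over CI) | Chance of at least one (range over CI) |
|---|---|---|
| 4 | 0.03 (0.01 to 0.10) | 3% (0.7% to 9%) |
| 14 | 0.12 (0.02 to 0.33) | 11% (2% to 29%) |
| 32 | 0.26 (0.05 to 0.76) | 23% (5% to 54%) |

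7. **Effect of a hold on DLT counting.** Related Grade 3-4 events in cycle 1 already qualify, so a hold at those grades adds none. A mandatory hold at Grade 2 could add some. Section 5.2 calls an event intolerable if more than 25% of dabrafenib or trametinib is missed in cycle 1, and 0.25 × 56 doses = 14 doses = 7 days. A Grade 2 hold longer than 7 days could therefore make the event a DLT.

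**The case against.** The strongest reply is that local therapy first is a reasonable clinical choice. Section 2.2.2.4 says these events responded to symptomatic treatment, mainly topical corticosteroids. In the randomized 150/2 arm of the doublet study every ocular event was Grade 1-2 except one Grade 3 RPED. RPED is a different event tied to a different drug, so Table 6-11 is only an analogy. Other rules in Section 6.1, such as those for QTc and venous thromboembolism, also lack CTCAE grade rows, so a missing split is not in itself an error. Section 2.3 favours continuing BRAF inhibition and reports accelerated progression after it is discontinued. With trametinib held under Table 6-10 and AT13387 interrupted under Table 6-15, a dabrafenib hold could stop all three drugs at once.

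Much of this stands. It supports leaving Grade 1-2 as it is and it makes the cost of a change real, although a short hold is not discontinuation. It does not explain why a listed event of special interest should have a weaker Grade 3-4 requirement than the protocol's own default.

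A reader might also infer that Tables 6-10 and 6-12 contradict each other at Grade 4, one interrupting trametinib and the other continuing treatment. The documents do not support that. Table 6-10 holds trametinib for a visual change, and the same cell hands uveitis or iritis to Table 6-12. What remains is the silence on resumption in step 4, and it applies at Grade 2-3 as well as Grade 4.

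**Conclusion.** The point holds as a gap in what is required: no rule makes the investigator hold dabrafenib at onset of Grade 3-4 uveitis or iritis, and up to 14 further doses may be taken before one does. It is a cheap improvement for a rare event, with 0.26 cases expected at full enrollment of 32.

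That figure assumes that 365 is the denominator for the 3 cases, that exposure resembles the doublet study (shorter exposure would lower it), and that AT13387 adds no uveitis risk. The percentages are chances of seeing a case, not of injury.

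Three stronger readings should be resisted. The protocol does not forbid an early hold, because its wording on dabrafenib is permissive and its general provisions allow one. Nothing in the documents shows that the first-week rule has harmed anyone, or lets such harm be estimated. The escalation rules, the MTD and the planned analyses are unaffected.

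**What to change.** In Table 6-12:
- **Grade 1-2:** keep the present rule.
- **Grade 3-4:** follow Table 6-1 for dabrafenib. Interrupt at onset, with permanent discontinuation as the alternative at Grade 4. Restart one dose level lower, only after the ocular inflammation resolves (Table 6-12's existing condition). Keep the 4-week discontinuation limit.
- **Trametinib:** state that resumption follows Table 6-10, including the medical-monitor discussion at Grade 4.
- **AT13387:** state that it follows Table 6-15, and correct the reference to Table 6-13 in Section 6.2.1.1.

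In Table 6-10, add that the permission to continue dabrafenib ends once Grade 3-4 uveitis or iritis is diagnosed.

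The cost is wording in the next amendment, with no new visits or procedures. The clinical downside is that a Grade 3-4 patient who would have improved within a week on topical therapy now has a dabrafenib hold and a one-level reduction. Section 6.1 allows re-escalation after 4 weeks at the reduced dose if the event has settled and no further toxicity appears. Confining the new hold to Grade 3-4 leaves DLT counting as it is.
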